8.2.1. Sensitivity Analyses of the Primary Efficacy Endpoint

8.2.1.1. Primary Sensitivity Analyses

Sensitivity analyses on the primary efficacy endpoint will be performed using the same ANCOVA model as the primary efficacy analysis with fixed effects for treatment group and the randomization stratification factors (CKD stage [CKD2 versus CKD3/4] and Mayo Clinic ADPKD Image Classification [1C, 1D, or 1E]) and the baseline eGFR as a covariate.

Two sensitivity analyses will be performed on the mITT:

- The annualized change in eGFR (2021 CKD-EPIcr_R) without restriction from baseline to off treatment assessment after Week 52 (mean of 3 eGFR values obtained during off-treatment follow-up visits after Week 52); missing data are handled by multiple imputation:
 - MAR (Section 6.1.4.1.1)
- The annualized change in eGFR (2021 CKD-EPIcr_R) with restriction from baseline to final assessment (mean of 3 eGFR values obtained during Follow-up Period I after Week 52 for on-treatment completers or, for participants who discontinue study drug treatment prior to Visit 22, during the Follow-up Period 8 to 28 days following study drug treatment discontinuation); missing data are handled by multiple imputation:
 - MAR (Section 6.1.4.1.1)
 - MNAR and tipping point analysis (Sections 6.1.4.1.2 & 6.1.4.1.3)

Two sensitivity analyses will be performed on the PEAS:

- The annualized change in off-treatment eGFR (2021 CKD-EPIcr_R) without restriction from baseline to final assessment (mean of 3 eGFR values obtained during Follow-up Period I after Week 52 for on-treatment completers or, for participants who discontinue study drug treatment prior to Visit 22, during the Follow-up Period 8 to 28 days following study drug treatment discontinuation)
- The annualized change in eGFR (2009 CKD-EPI) with restriction from baseline to final assessment (mean of 3 eGFR values obtained during Follow-up Period I after Week 52 for on-treatment completers or, for participants who discontinue study drug treatment prior to Visit 22, during the Follow-up Period 8 to 28 days following study drug treatment discontinuation)

One sensitivity analysis will be performed on the on-treatment completers of the PEAS :

• The annualized change in eGFR (2021 CKD-EPIcr_R) without restriction from baseline to final assessment (mean of 3 eGFR values obtained during Follow-up Period I after Week 52 for on-treatment completers or, for participants who discontinue study drug

treatment prior to Visit 22, during the Follow-up Period 8 to 28 days following study drug treatment discontinuation)

One sensitivity analysis will be performed on the PPAS:

• The annualized change in eGFR (2021 CKD-EPIcr_R) with restriction from baseline to final assessment (mean of 3 eGFR values obtained during Follow-up Period I after Week 52 for on-treatment completers or, for participants who discontinue study drug treatment prior to Visit 22, during the Follow-up Period 8 to 28 days following study drug treatment discontinuation)

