8.4.2 Sensitivity Analysis of the Primary Efficacy Analysis

In particular, in order to address the impact of missing data on the results from the primary efficacy analysis, a number of sensitivity analyses will be performed. The detailed sensitivity analyses for the primary efficacy analysis will be described in the statistical analysis plan (SAP).

Amongst these sensitivity analyses, the main sensitivity analysis of the primary efficacy analysis will use the mean of eGFR values obtained pretreatment and the mean of eGFR values obtained off treatment after the end of the 52-week treatment period, regardless of adherence to randomized treatment and/or withdrawal for all randomized participants, i.e., Intent-To-Treat participants. Missing values at Week 52 will be imputed using multiple imputations (assuming missing at random). Tipping point analyses will be included using a pattern-mixture model to impute missing data at Week 52 (assuming missing not at random) by systematically varying assumptions about the missing outcomes on the two treatment arms – these tipping point analyses will be bi-dimensional, i.e., allow the assumptions about the missing outcomes in the two arms to vary independently, and will include scenarios where the dropouts on the lixivaptan arm have worst outcome compared to placebo dropouts.

8.5 Secondary Efficacy Analyses.

If the primary efficacy analysis is statistically significant at the 1% level of significance, then the secondary efficacy endpoints of (1) annualized rate of change (slope) in eGFR based on all on-treatment eGFR determinations during the Double-blind, Randomized Treatment Period calculated from the CKD-EPI_{cr}_R equation for serum creatinine; and (2) annualized change in TKV as measured by MRI will be analyzed. Each will be tested at the 1% level of significance in sequential order using a closed testing procedure on the SEAS. The details of the testing procedure will be provided in the SAP for the study.

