6.1.4. Handling of Dropouts or Missing Data

Assessments are planned, by protocol, to be collected from all randomized participants except those who 1) withdraw consent AND 2) do not consent to any collection of data. Every effort will be made to keep randomized participants in the study and offer them options for continued treatment and, at a minimum, continued study participation to the degree possible; strategies of these efforts are described in the study protocol Section 4.2.4, Section 4.2.7, and Appendix 5 (Section 13.5) in order to minimize missing data. While all possible efforts will be made to ensure that participants stay in the study and all data is collected as scheduled, the occurrence of missing data cannot be completely eliminated.

The handling of missing data is dependent upon the efficacy analyses (see Section 8 Efficacy Analysis for detail). The missing data for efficacy analyses are generally imputed by the following methods:

• Missing at random (MAR) – mixed-effects model for repeated measures (MMRM): a modeling approach (missing data are not imputed prior to the analysis)

- Missing at random (MAR) multiple imputation (MI)
- Missing not at random (MNAR) multiple imputation (MI) with assumptions of missing not at random. Treatment impact on efficacy endpoints for missing data varies independently on the two treatment arms bi-dimensionally. Pattern-mixture approach is applied to investigate the MNAR pattern based on dropout reasons. Specifically, MNAR in the following patterns of dropout reasons will be investigated as MNAR:
 - Lack of efficacy (LOE)
 - LOE and adverse events (AE)
 - All dropouts

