6.1.4.1.2 MNAR Imputation

The MNAR imputation of missing data and data analysis are implemented as following:

- Using a standard MAR-based multiple imputation approach (See Section 6.1.4.1.1) to impute missing data to obtain 50 complete analysis data sets
- The imputed data for missing reason matching the MNAR pattern will be adjusted by the following:
 - If the participant is randomized in the lixivaptan group, the imputed value will be reduced by k (e.g., 50%) times the treatment difference (obtained using the MAR approach)
 - If the participant is randomized in the placebo group, the imputed value will be increased by 1 (e.g., 100%) times the treatment difference (obtained using the MAR approach)
 - k and l are independently determined
- Using the pre-specified analysis to analyze each set of the completed data along with the imputed data
- Obtaining the overall results using PROC MIANALYZE

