6.1.4.1.3 Tipping Point Analysis

As a sensitivity analysis to the multiple imputation analysis as described above in Section 6.1.4.1.2, a tipping point analysis will be performed in order to determine the robustness of the primary efficacy analysis.

A tipping point is the inflection point at which the inference under the MNAR assumption changes substantially (i.e., the specific k and l in MNAR imputation to reverse the statistical significance).

Since the missing data with the MNAR pattern are imputed bi-dimensionally, the tipping point curve will be determined for each of MNAR patterns by the following:

• Let 1 = 0%, 10%, 20%, 30%, 40%, 50%, 60%, 70%, 80%, 90%, 100%, 125%, 150%, 175%, 200%, 250%, 300%, 350%, 400%, 450%, and 500%.

Note that:

- \circ 1 = 0% (imputed missing in placebo as MAR)
- \circ 1 = 100% (imputed missing in placebo as lixivaptan)
- For each l, search a tipping point k by implementing k=0%, 10%, 20%, 30%, 40%, 50%, 60%, 70%, 80%, 90%, 100%, 125%, 150%, 175%, 200%, 250%, 300%, 350%, 400%, 450%, and 500%. Report the analysis results at the tipping point when a tipping point is found; otherwise, report the analysis results for k=500% when a tipping point is not reached.

Note that:

- \circ k = 0% (imputed missing in lixivaptan as MAR)
- \circ k = 100% (imputed missing in lixivaptan as placebo)

• The tipping point curve consists of all the paired points of k and l when the tipping point is found.

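### The SAP moves the tipping-point analysis from missing Week 52 eGFR to the final-assessment endpoint without listing the change, so discontinuers with an 8–28-day sample are never shifted

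*SAP*

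**What the plan says.** Protocol 8.4.2 defines the main sensitivity analysis of the primary result. It uses off-treatment eGFR after the 52-week period, "regardless of adherence to randomized treatment and/or withdrawal for all randomized participants, i.e., Intent-To-Treat participants". Missing Week 52 values are imputed under MAR. The section then adds: "Tipping point analyses will be included using a pattern-mixture model to impute missing data at Week 52 (assuming missing not at random"). The assumptions for the two arms vary independently and include "scenarios where the dropouts on the lixivaptan arm have worst outcome compared to placebo dropouts". The protocol synopsis says much the same.

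SAP 8.2.1.1 states: "Two sensitivity analyses will be performed on the mITT".
- The first is the annualized change to the off-treatment assessment after Week 52, without restriction. Only MAR imputation is listed under it.
- The second is the restricted annualized change to final assessment. For an early discontinuer this takes the samples from 8 to 28 days after stopping. MAR is listed, and so is "MNAR and tipping point analysis (Sections 6.1.4.1.2 & 6.1.4.1.3").

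SAP 6.1.4 says: "Pattern-mixture approach is applied to investigate the MNAR pattern based on dropout reasons". The patterns are lack of efficacy, lack of efficacy plus adverse events, and all dropouts. SAP 6.1.4.1.2 says: "The imputed data for missing reason matching the MNAR pattern will be adjusted by the following". SAP 6.1.4.1.3 runs the two shift factors, k (lixivaptan) and l (placebo), from 0% to 500% of the MAR treatment difference, with the instruction to "report the analysis results for k=500% when a tipping point is not reached".

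SAP Section 15 undertakes to document analyses that depart from the protocol. Its rows cover added analysis sets, the Part 2 sets, height-adjusted liver volume, percent change, lixivaptan-treated safety summaries and removal of the blinded sample size re-estimation. None concerns the tipping point.

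**The concern.** The protocol's tipping point asks how poor the unmeasured Week 52 outcomes of dropouts would have to be before the conclusion fails. In the SAP those outcomes are filled in under MAR and never stressed.

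The analysis that carries the stress test uses an endpoint on which most discontinuers should have data, because Protocol 4.2.4 schedules three off-treatment samples between Day 8 and Day 28 for every randomized participant who stops. Someone with such a sample has no imputed value, so k and l cannot act on that person. An all-dropouts pattern would then omit every dropout who was sampled.

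The population also changes from all randomized to mITT. Section 15 lists mITT as an added set but does not record this switch. A reader who relies on Section 15 would not learn of either change.

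**Working it through.** **Inputs**
- Difference 1.40 (absolute value), SD 6.20, α = 0.01, power 90%, ratio 2:1, 900 lixivaptan and 450 placebo: Protocol 8.1 and SAP 3.7. Two-sided testing is stated for TKV in Protocol 8.5.2 and is what reproduces the sample size.
- 90% completion of Part 1: protocol synopsis, Study Design.
- 50 imputations: SAP 6.1.4.1.1.
- 21 values each for k and l, so 21 × 21 = 441 pairs: SAP 6.1.4.1.3.
- Assumptions: the share of discontinuers with no Week 52 value, and equal missing shares per arm. The planned 1.40 and 6.20 belong to the primary endpoint and are carried over to the Week 52 endpoint.

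**The plan's own figure.** Placebo n = 1.5 × (2.576 + 1.282)² × 6.20² / 1.40² = 437.7, so 438, and 3 × 438 = 1314. This matches the plan.

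**Who is shifted.** 10% of 1350 = 135 discontinuers. If all give an 8–28-day sample, the SAP's tipping point shifts 0 of 135. On the Week 52 endpoint, those without a value are shifted:
- 25% lost: 34 people (2.5% of 1350)
- 50% lost: 68 people (5%)
- 100% lost: 135 people (10%)

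**Effect of the shift.** With missing shares m_L and m_P, MAR difference d, and k and l as proportions:
- Shifted estimate = d × (1 − m_L·k − m_P·l).
- Within-imputation variance W = (1/900 + 1/450) × pooled variance, where the pooled variance is 6.20² plus the arm-size-weighted average of m(1 − m)(shift × d)². With no missing data the SE is 6.2 × √(1/900 + 1/450) = 0.358.
- Between-imputation variance B = sum over arms of [m/(1 − m)] × 6.20²/n.
- Total variance = W + (1 + 1/50) × B. Significance is lost when z falls below 2.576.

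**Week 52 endpoint, d = 1.40**

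| Missing per arm | Pairs that tip, of 441 | Tipping starts near |
|---|---|---|
| 2.5% | 0 | – |
| 5% | 39 | k + l = 630% |
| 10% | 214 | k + l = 300% |

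On the diagonal, the first grid point to tip is k = l = 350% at 5% missing and k = l = 175% at 10%.

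**Relocated (final-assessment) analysis.** The sample-size allowance is 1350 − 1314 = 36, or 2.67%.
- Spread evenly, most extreme pair k = l = 500%: estimate 1.40 × (1 − 10 × 36/1350) = 1.027, SE 0.369, z = 2.78. No pair tips.
- The corner pair first tips when missingness exceeds about 3.2% per arm.
- All 36 missing in placebo (36/450 = 8%), l = 500%: estimate 1.40 × (1 − 5 × 0.08) = 0.84, SE 0.374, z = 2.25. With separate arm variances z is 2.22. Both tip.
- With even missingness, observed effects of about 0.93 to 1.29 are significant under MAR but tip at the corner. These are about 31% of significant trials.

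**Simulation check** (multiple imputation, 300 replicates, observed data fixed at the planned effect), mean z: 2.78 at 2.67% with k = l = 500%; 2.25 for placebo only with l = 500%; 2.65 and 2.46 at 5% with k = l = 300% and 350%; 2.58 and 2.40 at 10% with k = l = 150% and 175%. These agree with the formulas.

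**The case against.** The strongest case is that the SAP's placement is legitimate and arguably better aimed. Protocol 8.4.2 leaves the detail to the SAP, and Protocol 8.14 lets the SAP modify the planned analyses. The stated purpose is to examine how missing data affect the primary result. That result uses the final assessment under an estimand of full adherence, and its MAR assumption concerns missing final assessments, which is what the SAP stresses. A tip on the Week 52 endpoint would weaken a supportive treatment-policy result, not the primary one. No imputation-based tipping point moves observed values, so under the protocol too a discontinuer with a Week 52 value would stay put. The SAP keeps the Week 52 analysis regardless of adherence, and its imputation model includes treatment duration. Shifts of practical interest do not tip: at 10% missing, k = l = 100% gives z = 2.96.

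Most of this stands as a limit on the size of the problem. The move is not forbidden, the relocated analysis tests something relevant, and the gap concerns only discontinuers lost by Week 52. The 100% loss case is an upper bound, since Protocol 4.2.4 encourages discontinuers to remain in the study. None of it supplies the stress test of Week 52 values that the protocol specifies, and none of it explains why Section 15 is silent.

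**Conclusion.** The concern holds as a should-fix. The SAP drops the protocol's MNAR tipping point on missing Week 52 eGFR, narrows that analysis from all randomized participants to the mITT, and lists neither change. The substitute cannot reach any discontinuer with an 8–28-day sample. At the planned effect it is a weak test: no pair tips if the 36-participant allowance is missing evenly. It can tip with a smaller observed effect, more missing data, or missingness concentrated in placebo.

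How much the protocol's version would add depends on Week 52 retention, for which the documents give no figure. Under the assumed loss rates it ranges from no tipping pairs at 2.5% missing to 214 of 441 at 10%. SAP Section 12 states that only 5 participants were randomized and that no statistical analyses will be performed, so the fault lies in the plan and changes no reported result.

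**What to change.** In SAP 8.2.1.1, run the first analysis (annualized change to the off-treatment assessment after Week 52) on the ITT set. Add under it the line that now stands only under the second analysis, "MNAR and tipping point analysis (Sections 6.1.4.1.2 & 6.1.4.1.3"). Keep the final-assessment tipping point as an additional analysis and enter that addition in SAP Section 15 with a reason. The cost is SAP wording and re-use of code already planned. No new data are needed.

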8.2.1.2. Secondary Sensitivity Analyses

Sensitivity on the annualized change in eGFR (2021 CKD-EPIcr_R) with restriction from baseline to final assessment (mean of 3 eGFR values obtained during Follow-up Period I after Week 52 for on-treatment completers or, for participants who discontinue study drug treatment prior to Visit 22, during the Follow-up Period 8 to 28 days following study drug treatment discontinuation) using a weighted ANCOVA will be performed on the PEAS. The weighted analysis is based on the reciprocal of the estimated variance of the "estimated slopes" for participants based on individual off-treatment eGFR values obtained during Follow-up Period I after Week 52 for on-treatment completers or, for participants who discontinue study drug treatment prior to Visit 22, during the Follow-up Period 8 to 28 days following study drug treatment for participants based on individual off-treatment eGFR values obtained during Follow-up Period I after Week 52 for on-treatment completers or, for participants who discontinue study drug treatment prior to Visit 22, during the Follow-up Period 8 to 28 days following study drug treatment prior to Visit 22, during the Follow-up Period 8 to 28 days following study drug treatment discontinuation). The detailed algorithm to derive the weight is provided in an Appendix.

The weighted ANCOVA model will include fixed effects for treatment group and the randomization stratification factors (CKD stage [CKD2 versus CKD3/4] and Mayo Clinic ADPKD Image Classification [1C, 1D, or 1E]) and the baseline eGFR as a covariate.

8.2.1.3. Exploratory Sensitivity Analysis

The annualized change from baseline in eGFR theoretically contains natural disease progression due to no treatment such as a period for placebo run-in or a period between the last treatment and serum creatinine assessment. To explore the hypothetical treatment effect, a sensitivity analysis will also be performed on the PEAS based on all the changes from baseline in off-treatment eGFRs (2021 CKD-EPIcr_R) that are assessed after 8 days off treatment after randomization in Part 1. The linear mixed effect model with effects of pre-randomization time, off-treatment time, on-treatment time, treatment-by-on-treatment time, randomization stratification factors (CKD stage [CKD2 versus CKD3/4] and Mayo Clinic ADPKD Image Classification [1C, 1D, or 1E]), and eGFR baseline will be used to fit the eGFR data. Intercept, pre-randomization time are both a fixed effect and a random effect. An unstructured variance-covariance matrix is used for modeling.

PROC MIXED EMPIRICAL;

CLASS TREATMENT CKD_STAGE MAYO_CLASS USUBJID; MODEL CHANGE = BASELINE PRIOR-TIME OFF-TIME ON-TIME ON-TIME*TREATMENT CKD_STAGE MAYO_CLASS;

RANDOM INTERCEPT PRIOR-TIME/TYPE=UN SUB= USUBJID; ESTIMATE "Annualized Change from Baseline in eGFR in Lixivaptan Group" BASELINE 1 ON-TIME 1 ON-TIME*TREATMENT 0 1; ESTIMATE " Annualized Change from Baseline in eGFR in Placebo Group " BASELINE 1 ON-TIME 1 ON-TIME*TREATMENT 1 0;

ESTIMATE "Treatment Difference in Annualized Slope of On-Treatment eGFR" ON-TIME*TREATMENT -1 1;

RUN;

where:

- Treatment group (TREATMENT) is coded as 0=Placebo and 1=lixivaptan
- Total time (years) for each off-treatment eGFR = elapsed time from baseline [median date of 3 baseline eGFRs obtained during Screening and Placebo Run-In Periods (Visits1a [1b, if required], Visit 2, and Visit 3) to time of off-treatment eGFR (≥ 8 days off treatment). Total time is divided into three portions: pre-randomization time (PRIOR-TIME), on-treatment time (ON-TIME) and off-treatment time (OFF-TIME).
- Pre-randomization time (years) = elapsed time (years) from baseline to date of randomization
- On-treatment time (years) = time (years) on treatment after randomization, number of treated days with randomized treatment from randomization to date of eGFR assessment/365.25.
- Off-treatment time (years) = Total time (years) for each off-treatment eGFR Prerandomization time (years) - On-treatment time (years).

8.3. Secondary Efficacy Analysis (Part 1)

If the primary efficacy endpoint is statistically significant at the 1% level of significance, then the secondary efficacy endpoints will be tested at the 1% level of significance in sequential order on the SEAS:

- 1. Annualized rate of change (slope) in eGFR based on all on-treatment eGFR (2021 CKD-EPIcr_R) determinations during the Double-blind, Randomized Treatment Period
- 2. Annualized percent change from baseline in htTKV as measured by MRI

Because the testing is sequential, the type I error rate of ≤ 0.01 is maintained. Failure at any stage in the sequence implies automatic failure at all subsequent stages. If the primary efficacy endpoint is not significant at the 1% level of significance then all other p-values will be presented as exploratory only.

If the primary efficacy endpoint is significant at the 1% level of significance, the first secondary efficacy endpoint will be tested. If the first secondary efficacy endpoint is significant at the 1% level of significance, the second efficacy endpoint will be tested. If the first secondary efficacy endpoint is not significant at the 1% level of significance, the second secondary efficacy endpoint is presented for exploratory purposes only.

8.3.1. Annualized Rate of Change (Slope) in eGFR

The first secondary efficacy endpoint is annualized rate of change (slope) in eGFR (2021 CKD-EPIcr_R) at on-treatment timepoints using the SEAS. This annualized rate of change (slope) in eGFR on treatment will be estimated by utilizing a mixed-effects model for repeated measures (MMRM) on the observed changes in eGFR from baseline (mean of the 3 eGFR values obtained during the Screening and Placebo Run-in Periods) to all visits with on-treatment eGFR values during the Double-Blind, Randomized Treatment Period visits, i.e., Visit 10 (Week 4) to Visit 22 (Week 52), while on study drug treatment. Any eGFR values obtained 1 day after study drug treatment during the Double-Blind, Randomized Treatment Period are excluded from the analysis. The MMRM will include treatment group, visit, treatment group-by-visit, and randomization stratification factors (CKD stage [CKD2 versus CKD3/4] and Mayo Clinic ADPKD Image Classification [1C, 1D, or 1E]) as fixed effects, baseline eGFR as a covariate, and the baseline-by-visit interaction. An unstructured variance-covariance matrix is assumed for the repeated measures.

Analysis of MMRM will be applied to the change from baseline in eGFR among the 13 ontreatment visits: visit 10 (week 4), visit 11 (week 8),visit 12 (week 12), visit 13 (week 16), visit 14 (week 20), visit 15 (week 24), visit 16 (week 28), visit 17 (week 32), visit 18 (week 36), visit 19 (week 40), visit 20 (week 44), visit 21 (week 48) and visit 22 (week 52). The median of the 13 visits is the 7th visit, i.e., Visit 16 (Week 28).

To estimate the slope in eGFR on treatment, the contrast coefficients of the linear trend for visits will become -6, -5, -4, -3, -2, -1, 0, 1, 2, 3, 4, 5, 6. Under assumptions that the annualized slope and acute hemodynamic effect are constant over time, this contrast can be used to estimate the slope (note that the acute hemodynamic effect is eliminated by the contrast). The resulted estimate corresponding to those coefficients will be slope (per week) multiplied by 728 (-6*4 - 5*8 -4*12 -3*16 -2*20 -1*24 +0*28 +1*32 +2*36 +3*40 +4*44 +5*48 +6*52=728) or annualized slope multiplied by 14 (728/52=14).

Thus, the coefficients of the linear trend contrast of these 13 visits to estimate the annualized slope are -6/14, -5/14, -4/14, -3/14, -2/14, -1/14, 0/14, 1/14, 2/14, 3/14, 4/14, 5/14, 6/14.

Example SAS code is shown below:

```
PROC MIXED EMPIRICAL;
```

RUN;

```
CLASS TREATMENT VISIT CKD_STAGE MAYO_CLASS USUBJID;

MODEL CHANGE = TREATMENT BASELINE VISIT VISIT*TREATMENT BASELINE*VISIT CKD_STAGE

MAYO_CLASS /SOLUTION;

REPEATED VISIT/TYPE=UN SUB= USUBJID;

ESTIMATE "Lixivaptan Annualized Slope" VISIT -6 -5 -4 -3 -2 -1 0 1 2 3 4 5 6

VISIT*TREATMENT 0 0 0 0 0 0 0 0 0 0 0 0 -6 -5 -4 -3 -2 -1 0 1 2 3 4 5 6/DIVISOR=14;

ESTIMATE "Placebo Annualized Slope" VISIT -6 -5 -4 -3 -2 -1 0 1 2 3 4 5 6

VISIT*TREATMENT -6 -5 -4 -3 -2 -1 0 1 2 3 4 5 6 0 0 0 0 0 0 0 0 0 0 0 /DIVISOR=14;

ESTIMATE "Treatment Difference in Annualized Slope"

VISIT*TREATMENT 6 5 4 3 2 1 0 -1 -2 -3 -4 -5 -6 -6 -5 -4 -3 -2 -1 0 1 2 3 4 5 6/DIVISOR=14;
```

A linear contrast of the treatment slope differences for visits will be used for this analysis.

